## ABBREVIATIONS

AE	Adverse event
AUC	Area under the curve
CAEPR	Comprehensive Adverse Events and Potential Risks
CFR	Code of federal regulation
cGMP	current Good Manufacturing Practice
CTCAE	Common Terminology Criteria for Adverse Events
CTEP	Cancer Therapy Evaluation Program
CIP	Cancer Imaging Program
cm	Centimeter
COV	Coefficient of variation
CT	Computed tomography
DCE-MRI	Dynamic contrast enhanced magnetic resonance imaging
DCIS	Ductal carcinoma in situ
DICOM	Digital imaging and communications in medicine
DOT	Disease Oriented Team
DSMC	Data and Safety Monitoring Committee
DWI	Diffusion weighted imaging
ECOG/ACRIN	Eastern Cooperative Oncology Group/American College of Radiology Imaging Network
ER $\alpha$ +	Estrogen receptor alpha-positive
FDA	U.S. Food and Drug Administration
FDG	$^{18}\text{F}$ -fluorodeoxyglucose
FES	$^{18}\text{F}$ -fluoroestradiol
GCP	Good Clinical Practice
GE	General Electric
H&E	hematoxylin and eosin
HER2	Human epidermal growth factor receptor 2
HIPAA	Health Insurance Portability and Accountability Act
HPLC	High performance liquid chromatography
ICC	Intra-class correlation coefficient
IHC	Immunohistochemistry
IME	Important medical event
IND	Investigational new drug
IRB	Institutional review board
IV	Intravenous
Kg	Kilogram
M	molar
MBq	MegaBecquerel
mCi	MilliCurie
mGy	MilliGray
mL	Milliliter
mmol	millimole
mrem	milli Roentgen equivalent man
MRI	Magnetic resonance imaging

MRN	Medical record number
MR/PET	Magnetic resonance/Positron emission tomography
mSv	MilliSievert
MTV	Metabolic tumor volume
NCI	National Cancer Institute
oz	ounce
PACS	Picture archiving and communication system
PET	Positron emission tomography
PET/MRI	Positron Emission Tomography/Magnetic Resonance Imaging
PSR	Protocol summary report
PI	Principal investigator
PR	Progesterone receptor
QA	Quality Assurance
QC	Quality Control
ROC	Receiver operator curve
ROI	Region of interest
SAE	Serious adverse event
SBP/SHBG	Sex steroid-binding protein/Sex hormone binding globulin
SUV	Standard uptake value
TLU	Total lesion uptake
TRIP	Translational Research Initiatives in Pathology
USP	United States Pharmacopeia
UW	University of Wisconsin
UWCCC	University of Wisconsin Carbone Cancer Center

## 1. PROTOCOL SUMMARY

### TITLE OF STUDY

Hybrid Molecular Imaging of Estrogen Receptor in Breast Cancer Patients with Ductal Carcinoma In Situ

### CLINICAL PHASE

Phase 2

### PERIOD OF TRIAL

Planned study conduct duration of approximately 3 years.

### STUDY OBJECTIVES

Integrated whole-body magnetic resonance imaging (MRI)-positron emission tomography (PET) scanners have recently been introduced for clinical use. This technology combines the anatomic and perfusion data obtained with Dynamic Contrast Enhanced (DCE) MRI with functional imaging data obtained from PET. For breast imaging, the combination of MRI and PET has important potential to improve diagnostic accuracy and provide molecular characterization of breast cancer. The overall purpose of this research is to determine the technical feasibility of simultaneous breast DCE MRI with  $^{18}\text{F}$ -FES PET for measuring estrogen receptor (ER) in patients with ductal carcinoma in situ (DCIS) and identifying patients with low-risk of disease recurrence. We hypothesize that quantitative  $^{18}\text{F}$ -FES uptake parameters from PET/MRI will correlate well with the ER immunohistochemistry score and with low-risk recurrence scores.

#### Primary Objective

To compare quantitative  $^{18}\text{F}$ -FES uptake of biopsy-proven DCIS measured using PET/MRI with ER protein levels determined by immunohistochemistry.

#### Secondary Objectives

- 1) To determine the optimal cut-point  $^{18}\text{F}$ -FES uptake value for distinguishing between ER+ and ER-negative DCIS; 2) to determine the test-retest reproducibility of quantitative assessment of tumor  $^{18}\text{F}$ -FES uptake; 3) to determine the optimal cut-point  $^{18}\text{F}$ -FES uptake value for distinguishing between low-risk DCIS and intermediate/high-risk DCIS; 4) to estimate the association of quantitative  $^{18}\text{F}$ -FES uptake (continuous SUVmax) with research-based Oncotype DX DCIS scores (0-100); 5) to measure the upgrade rate to invasive cancer at surgical excision; 6) to correlate tumor  $^{18}\text{F}$ -FES uptake with serum estradiol and sex hormone binding globulin levels.

#### Exploratory Objective

To correlate tumor cell density with F-FES uptake on PET/MRI.

## INCLUSION CRITERIA

- Women 18 years of age or older
- Diagnosis of biopsy-proven DCIS without invasion or microinvasion measuring at least 1.0 cm in diameter by any imaging modality
- Undergoing diagnostic breast MRI ordered by the referring clinician for staging and extent of disease\*

## EXCLUSION CRITERIA

- Inability or unwillingness to provide informed consent to the study
- Surgery, radiation, neoadjuvant chemo/endocrine therapy for the current malignancy prior to study enrollment
- Patients currently taking or have taken an ER-blocking medication (e.g. tamoxifen, raloxifene) within 6 weeks prior to study enrollment
- Pregnant or lactating women
- Patient with intolerance or contraindications for MRI or gadolinium-based contrast agents
- Patient girth exceeds the bore of the MRI/PET scanner
- Patients with a history of allergic reaction attributable to compounds of similar chemical or biologic composition to F-FES
- Patients in liver failure as judged by the patient's physician, due to the hepatobiliary clearance of F-FES
- Patients requiring intravenous (IV) conscious sedation for imaging are not eligible; patients requiring mild, oral anxiolytics for the clinical MRI will be allowed to participate as long as the following criteria are met:
  - The subject has their own prescription for the medication
  - The informed consent process is conducted prior to the self-administration of this medication
  - They come to the research visit with a driver or an alternative plan for transportation (e.g. Uber, taxi, etc.)

## STUDY DESIGN

This is a prospective, one-arm, observational study which will enroll patients with biopsy-proven DCIS scheduled for diagnostic breast MRI for preoperative staging/extent of disease evaluation as part of standard of care. Eligible patients will be consented for participation in the research study which includes a directed breast PET/MRI with F-FES. F-FES uptake of the known malignancy will be measured on the PET/MRI examination using standardized uptake values (SUV) and tumor-to-normal tissue ratios. The proposed work-flow is described in the schema.

---

[figure not shown]
\* Patients with newly diagnosed DCIS from a screening breast MRI are also eligible to participate in this study. For these subjects, the research breast PET/MRI should be performed prior to any treatment or surgery for DCIS.

## NUMBER OF SUBJECTS

We will test the hypothesis that  $^{18}\text{F}$ -FES  $\text{SUV}_{\text{max}}$  from PET/MRI correlates well against the ER IHC Allred score. The correlation of the two measures will be evaluated using Spearman correlation analysis. A sample size of 12 patients achieves 82% power ( $\beta=0.20$ ) for detecting an expected correlation coefficient ( $r=0.73$ ) to be significantly different from zero with two-tailed  $\alpha$  value of 0.05.

We anticipate enrolling approximately 1 subject every 1-2 months . To measure test-retest reproducibility, a subset of up to 5 participants with ER+ DCIS will have the option to for both test-retest FES scans. The number of subjects with ER-negative DCIS will be limited to  $\leq 3$ .

## SCHEMA

## 2. INTRODUCTION

DCIS comprises up to one-fourth of all newly diagnosed cases of breast cancer (1). The incidence of DCIS has markedly increased since the widespread utilization of screening mammography. It is estimated that approximately 63,410 new cases of in situ carcinoma will be diagnosed in the United States in 2017 (2). Despite the high prevalence of DCIS, overall treatment outcomes are excellent with 3.3% breast-cancer specific mortality after 20 years (3).

DCIS is a non-obligate precursor to invasive breast cancer, meaning some disease will remain DCIS if not surgically excised while others will progress to invasive cancer (4, 5). Small study series of the natural history of DCIS have found that approximately 28% (7/25) of untreated DCIS progressed to invasive disease within 15 years (6). Even cases of low nuclear grade DCIS have been shown to develop into invasive breast cancer in 36% (16/45) of patients undergoing biopsy only (7). In contrast, data also exist from autopsy studies that have found undiagnosed DCIS in up to 15% of women who died from causes other than breast cancer (8).

The conventional treatment of DCIS is surgical excision, either through lumpectomy or mastectomy (9). For patients eligible for breast conserving surgery, radiation therapy is typically recommended after lumpectomy (10) since adjuvant radiotherapy has been shown to reduce the risk of local recurrence (either recurrent DCIS or invasive cancer) by approximately 50% (11). Compilation of data from four randomized trials consisting of 3,729 women with DCIS have shown that radiation therapy reduced the ten-year rate of local recurrence from 28.1% in patients randomized to surgery alone versus 12.9% for those randomized to surgery with radiation therapy (11). Adjuvant endocrine therapy (tamoxifen or aromatase inhibitors) can also be considered as an additional systemic risk-reducing treatment option in women with estrogen receptor (ER) positive DCIS (12-16).

In contrast with invasive breast cancer, use of adjuvant radiotherapy or endocrine therapy for DCIS patients has not yet been shown to improve survival (11, 12). Thus, the potential for over-diagnosis and over-treatment of DCIS has become a controversial topic. Improved individualized treatment plans for women with DCIS and prevention of over-treatment in patients with “low-risk” DCIS has been ranked highly as a critical and impactful research priority (17-20). There are ongoing clinical trials evaluating the comparative effectiveness of treatments that are alternatives to the standard described above. These include the E4112 trial, which seeks to avoid radiation therapy in women with low risk DCIS and the COMET trial which is evaluating endocrine therapy as an alternative local control approach for women with ER/PR+ low and intermediate grade pure DCIS.

Current approaches for risk stratification are primarily based on clinical and pathological factors. These include patient age, nuclear grade, size, and surgical margin status. Prognostic models, such as the University of Southern California/Van Nuys Prognostic Index (21) and the Memorial Sloan-Kettering Cancer Center Nomogram (22), have been developed that incorporate these clinicopathologic variables. These models are available to clinicians to provide a patient with information regarding the probability of local

recurrence with and without adjuvant therapy to facilitate shared decision-making. A drawback of this approach is that the methods have not been fully validated using independent data sets outside of the institutions from which they were developed (23, 24).

A multigene expression assay has been recently developed that provides a ten-year risk estimate of local recurrence for DCIS patients following breast conserving therapy alone (25). The 12-gene Oncotype DX DCIS Score is generated from expression levels of seven cancer related genes and five reference genes determined from a patient's biopsy or surgical specimen (25). The score is a continuous variable from 0 to 100. Low-risk scores are 0 to 38. Intermediate-risk scores are 39 to 54. High-risk scores are 55 to 100. The score was initially validated using data from the Eastern Cooperative Oncology Group (ECOG) E5194 clinical trial, a prospective cohort study of 327 patients deemed to have low-risk of local recurrence based on clinicopathologic features treated with breast conserving surgery alone. The 10-year risks (95%CI) of any ipsilateral breast event (local recurrence of DCIS or invasive carcinoma) for low, intermediate, and high risk scores were 10.6% (6.9-16.2%), 26.7% (16.2-41.9%) and 25.9% (14.8-43%), respectively and 3.7% (1.8-7.7%), 12.3% (5.1-27.8%), and 19.2% (9.5-36.4%), respectively, for an invasive ipsilateral breast event (25). The DCIS score was further validated in a more diverse patient population treated with breast conserving surgery alone, the Ontario DCIS cohort (26, 27). The 10-year risks (95% CI) of any ipsilateral breast event for these 571 patients with low, intermediate, and high risk scores were 12.7% (9.5-16.9%), 33.0% (23.6-44.8%), and 27.8% (20.0-37.8%), respectively (26). Thus, this genomic test has been shown to provide information on local recurrence independent of traditional clinicopathologic factors such as age, size, and grade (25, 26) and has been shown to have clinical utility in influencing patient management (28, 29). However, the test is expensive (~\$3500) and may not be cost effective (30). Furthermore, it requires a 3-week turnaround time (29) and sufficient tissue for analysis which may introduce sampling bias.

An important molecular target in premalignant and malignant breast tissue is ER, which drives hormone-dependent breast tumor growth, and can be inhibited by endocrine therapy. As shown in invasive breast cancer, ER appears to be an important prognostic factor and predictive biomarker for clinical benefit of adjuvant tamoxifen treatment for DCIS (16). In normal breast tissue, ER is expressed in a minority of cells at low to moderate staining intensity. However, very high levels of ER expression in nearly all cells are noted in most premalignant and noninvasive breast lesions (e.g. hyperplasias, atypia, lobular carcinoma in situ, and non-comedo DCIS) (31). The majority of DCIS express ER protein (approximately 69%; range 49-97%) (32). The exception is high grade comedo DCIS which can have low or no ER expression. Semi-quantitative ER levels measured by immunohistochemistry in DCIS are inversely related to the histologic grade of DCIS and are increased compared to invasive breast cancer (33). Interestingly, tumors cells at sites of focally disrupted myoepithelial cell layers are predominately (86.4%) ER-negative (34).

Expression of ER can be measured in patients through the use of a radiolabeled estrogen ligand, 16 $\alpha$ -F-fluoro-17 $\beta$ -estradiol (F-FES), and positron emission tomography (PET)

imaging (35, 36). Tumoral  $^{18}\text{F}$ -FES uptake, as measured by  $\text{SUV}_{\text{max}}$  with whole body PET/CT imaging, correlates well ( $r=0.56\text{--}0.96$ ) with ER expression in invasive breast cancer, as measured by radioligand binding in fresh tissue and immunohistochemistry in fixed tissue (37, 38). Overall sensitivity of  $^{18}\text{F}$ -FES PET for detection of ER+ breast cancer was 84% (95% CI: 73–91) in four published studies involving 114 patients (35, 37–40). Overall specificity was high at 98% (95% CI: 90–100) demonstrated by absence of  $^{18}\text{F}$ -FES uptake ( $\text{SUV}_{\text{max}}$  less than 1.0) in 51 of 52 histologically benign lesions and ER-negative breast cancer in three studies (35, 38–40).

$^{18}\text{F}$ -FES PET imaging has been studied as a predictive factor for clinical benefit of endocrine therapy in patients with metastatic ER+ breast cancer (35, 36). Van Kruchten *et al.* combined the results of four single-institution studies and determined that lack of response to endocrine therapy was predicted by  $^{18}\text{F}$ -FES  $\text{SUV}_{\text{max}}$  under 1.5 in this heterogeneous group of ER+ patients (35). Using the 1.5  $\text{SUV}_{\text{max}}$  threshold, 96 of 114 patients would have been selected to receive endocrine therapy, and 62 of these would have had a clinical benefit (PPV of 65%). Alternatively, of the 42 patients with  $^{18}\text{F}$ -FES  $\text{SUV}$  below 1.5, 37 derived no clinical benefit from endocrine therapy (NPV 88%).

The addition of magnetic resonance imaging (MRI) provides exquisite anatomic detail to characterize tumor morphologic characteristics and for functional assessment of lesion perfusion (41). In addition to anatomic data, certain advanced MRI techniques, such as diffusion weighted imaging, has potential to distinguish low versus high risk DCIS (42, 43). The ECOG/ACRIN trial E4112 titled “Prospective Study of Magnetic Resonance Imaging (MRI) and Multiparameter Gene Expression Assay in Ductal Carcinoma In Situ (DCIS)” is a multi-institutional study of 368 patients and includes a secondary outcome measure assessing the relation between MRI morphologic and kinetic features and DCIS score.

To the best of our knowledge, no studies have been performed using  $^{18}\text{F}$ -FES in patients with DCIS. This study will investigate the technical feasibility of simultaneous breast DCE MRI with  $^{18}\text{F}$ -FES PET for quantifying ER in patients with DCIS and identifying patients with low-risk of disease recurrence. If successful, we will pursue further studies using this imaging approach for stratifying patients with ER+ DCIS who may avoid radiation therapy (as in the E4112 study) and/or surgery (as in the COMET trial) and potentially derive the most benefit from endocrine therapy.

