### **3.2 Secondary objectives:**

- Determine the optimal cut-point  $^{18}\text{F}$ -FES uptake value for distinguishing between ER+ and ER-negative DCIS.
- Determine the test-retest reproducibility of quantitative assessment of tumor  $^{18}\text{F}$ -FES uptake.
- Determine the optimal cut-point  $^{18}\text{F}$ -FES uptake value for distinguishing between low-risk DCIS and intermediate/high-risk DCIS.
- Estimate the association of quantitative  $^{18}\text{F}$ -FES uptake (continuous  $\text{SUV}_{\text{max}}$ ) with research-based Oncotype DX DCIS scores (0-100)
- Measure the upgrade rate to invasive cancer at surgical excision.
- To correlate tumor  $^{18}\text{F}$ -FES uptake with serum estradiol and sex hormone binding globulin levels.

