## 12. STATISTICAL CONSIDERATIONS

### 12.1 Primary Objective

*To compare quantitative  $^{18}\text{F}$ -FES uptake of biopsy-proven DCIS measured using PET/MRI with ER protein levels determined by immunohistochemistry.*

The primary objective is to compare  $^{18}\text{F}$ -FES  $\text{SUV}_{\max}$  from PET/MRI with the ER immunohistochemistry semi-quantitative score obtained by using the Allred score. We will test the hypothesis that  $^{18}\text{F}$ -FES  $\text{SUV}_{\max}$  from PET/MRI correlates well against the ER IHC Allred score. The correlation of the two measures will be evaluated using Spearman correlation. The null hypothesis is  $H_0: p_0=0.00$  and the alternative hypothesis is  $H_1: p_1=0.73$ .

A sample size of 12 patients achieves 82% power ( $\beta=0.20$ ) for detecting an expected correlation coefficient ( $r=0.73$ ) to be significantly different from zero with two-tailed  $\alpha$  value of 0.05 (<http://www.sample-size.net/correlation-sample-size/>). We anticipate enrolling 1 subject every 1-2 months. The number of subjects with ER-negative DCIS will be limited to  $\leq 3$ .

Other measures of  $^{18}\text{F}$ -FES uptake including  $\text{SUV}_{\text{peak}}$ ,  $\text{SUV}_{\text{mean}}$ , tumor-to-normal tissue uptake ratio, and total lesion uptake will also be correlated with the ER immunohistochemistry semi-quantitative score obtained by using the Allred score.

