## 12.2 Secondary Objectives

1. To determine the optimal cut-point  $^{18}\text{F}$ -FES uptake value for distinguishing between ER+ and ER-negative DCIS.

Receiver operating characteristic (ROC) curve analysis will be performed to determine the optimal cut-point for  $^{18}\text{F}$ -FES uptake to distinguish ER+ from ER-negative DCIS, as defined by the clinical pathology report. The area under the curve (AUC) for the ROCs and their respective two-sided 95% confidence intervals will be calculated using logistic regression. The optimal cut-off point will be determined by considering the  $^{18}\text{F}$ -FES uptake value with the maximum sensitivity and specificity.

2. To determine the test-retest reproducibility of quantitative assessment of tumor  $^{18}\text{F}$ -FES uptake.

The reproducibility of the two measurements (test-retest) of  $^{18}\text{F}$ -FES uptake in the subjects (up to 5) who elect to undergo a second imaging session will be assessed by intra-class correlation coefficient (ICC) and its 95% confidence interval (47). Additionally, the coefficient of repeatability (CR) and the Bland-Altman plot will be used (48).

3. To determine the optimal cut-point  $^{18}\text{F}$ -FES uptake value for distinguishing between low-risk DCIS and intermediate/high-risk DCIS.

ROC curve analysis will be performed to determine the optimal cut-point for  $^{18}\text{F}$ -FES  $\text{SUV}_{\text{max}}$  to distinguish low-risk DCIS and intermediate/high-risk DCIS. Risk categories will be determined using the Van Nuys Prognostic Index, the Memorial Sloan-Kettering Cancer Center Nomogram, and the research-based Oncotype DX DCIS score. Sensitivity and specificity will be determined with two-sided 95% confidence intervals. The AUCs for the ROCs and their respective two-sided 95% confidence intervals will be calculated using logistic regression.

The optimal cut-off point will be determined by considering the  $^{18}\text{F}$ -FES uptake value with the maximum sensitivity and specificity.

This analysis will be done separately for each risk assessment model.

4. To estimate the association of quantitative  $^{18}\text{F}$ -FES uptake (continuous  $\text{SUV}_{\text{max}}$ ) with research-based Oncotype DX DCIS scores (0-100).

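### Objectives 3 and 4 pool ER+ and ER-negative lesions; adding ER+-only estimates would match the follow-on use in ER+ DCIS at little cost

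*Combined protocol and SAP*

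**What the plan says.** - **Follow-on use.** The last paragraph of section 2 (Introduction) names the next step: "If successful, we will pursue further studies using this imaging approach for stratifying patients with ER+ DCIS who may avoid radiation therapy". The same sentence also mentions avoiding surgery.
- **Who is enrolled.** Eligibility (section 4.1) does not depend on ER status. On ER-negative disease, the summary under Number of Subjects says "The number of subjects with ER-negative DCIS will be limited to" three or fewer; section 12.1 repeats the cap.
- **Objective 3.** Section 3.2 seeks the optimal "uptake value for distinguishing between low-risk DCIS and intermediate/high-risk DCIS". Section 12.2 item 3 plans an ROC analysis of SUVmax "to distinguish low-risk DCIS and intermediate/high-risk DCIS", once for each of three risk models: the Van Nuys index, the Memorial Sloan-Kettering nomogram and the research-based Oncotype DX DCIS score. Risk model is the only split named.
- **Objective 4.** Section 12.2 item 4 plans one correlation of SUVmax with the Oncotype score, also without reference to ER status.
- **Background.** Section 2 states: "Semi-quantitative ER levels measured by immunohistochemistry in DCIS are inversely related to the histologic grade of DCIS". It adds that high-grade comedo DCIS can lack ER, that FES uptake was absent in 51 of 52 benign lesions and ER-negative cancers, and that nuclear grade is one of the clinicopathologic risk factors.

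**The concern.** On the protocol's own background, an ER-negative lesion plausibly combines low FES uptake with higher grade, and so a higher clinicopathologic risk category. A few such lesions among 12 can produce an apparent association between FES uptake and risk even when uptake says nothing about risk among ER+ patients. To that extent objective 3 would repeat objective 1 (ER+ versus ER-negative) under a risk label.

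At stake is how the result is read. A favourable pooled AUC or correlation could be taken as support for follow-on work in ER+ patients while resting partly on patients outside that group. The plan specifies no estimate that would show whether this had happened.

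**Working it through.** **The plan's own figure.** The only quantified design claim is for the primary correlation: "A sample size of 12 patients achieves 82% power" for r = 0.73, two-sided alpha 0.05. By Fisher's z, atanh(0.73) = 0.929 and 0.929 × √9 − 1.96 = 0.826, giving 79.6% power. Adding the bias term 0.73/(2 × 11) = 0.033 gives 82.3%, so the stated figure reproduces. The plan gives no AUC or precision target for objectives 3 and 4, so the rest is illustration.

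**Inputs from the documents.** N = 12; at most 3 ER-negative; about 69% of DCIS is ER+ (range 49-97%); FES sensitivity 84% and specificity 98% (section 2).

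**Assumptions.** One lesion per subject; no FES-risk association within ER+; a chosen risk split; a chosen number of ER-negative lesions that are higher-risk (intermediate/high).

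**Is the cap likely to be reached?** With 31% ER-negative, the chance of 3 or more among 12 unselected patients is 77%. Over the cited prevalence range it runs from 0.5% (3% ER-negative) to 98% (51% ER-negative).

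**ER separation.** d = z(0.84) + z(0.98) = 0.994 + 2.054 = 3.05 SD. The AUC for ER+ versus ER-negative is A = Φ(3.05/√2) = 0.984.

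**Pooled AUC, all k ER-negative lesions higher-risk, m higher-risk lesions in total:** AUC = [kA + (m − k) × 0.5]/m.

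| k | m | A | Expected pooled AUC |
|---|---|---|---|
| 3 | 6 | 0.984 | (2.953 + 1.5)/6 = 0.74 |
| 3 | 5 | 0.984 | 0.79 |
| 3 | 7 | 0.984 | 0.71 |
| 2 | 5 | 0.984 | 0.69 |
| 1 | 4 | 0.984 | 0.62 |
| 3 | 4 | 1 | 0.875 |

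**Some ER-negative lesions low-risk** (A = 0.984; 3 ER+ higher-risk and 6 ER+ low-risk throughout), counting pairs:

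- One of three low-risk (5 versus 7, 35 pairs): (12 × 0.984 + 2 × 0.5 + 18 × 0.5 + 3 × 0.016)/35 = 0.62.
- Two of three low-risk (4 versus 8, 32 pairs): (6 × 0.984 + 2 × 0.5 + 18 × 0.5 + 6 × 0.016)/32 = 0.50.

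**Weaker ER separation** (k = 3, m = 6): 1.0 SD gives 0.63 and 1.5 SD gives 0.68.

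**Sampling variation in the 0.74 case.** In simulated trials the pooled AUC reached 0.70 in 62%. The ER+-only AUC, truly 0.50, did so in 19%. The cut-point maximising sensitivity plus specificity fell below every ER+ lesion in about half of the trials.

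**Precision (Hanley-McNeil).** Pooled 0.742 at 6 versus 6: SE 0.149, 95% CI about 0.45 to 1.0. ER+-only 0.50 at 3 versus 6: SE 0.215, 95% CI about 0.08 to 0.92.

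**Objective 4, extreme case.** The three ER-negative lesions hold the lowest SUVmax ranks (mean 2) and the highest score ranks (mean 11); the nine ER+ lesions have mean ranks 8 and 5; the overall mean is 6.5. Expected rho = [3 × (−4.5)(4.5) + 9 × (1.5)(−1.5)]/143 = −81/143 = −0.57, nominally significant in about 45% of simulated trials. With 3.05 SD separation and ER-negative scores only 1 SD higher, mean rho is about −0.28, significant in 13-14%.

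**The case against.** **The pooled analysis answers the stated question.** Objectives 3 and 4 are written for DCIS, not ER+ DCIS, and the study's purpose is technical feasibility. The Introduction sentence concerns later studies and sets no go/no-go rule. This stands: a reader might infer that items 3 and 4 are the wrong analyses, and the documents do not support that.

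**The 0.74 rests on stacked assumptions.** It needs three ER-negative lesions, all higher-risk, a 6/6 split the documents do not give, and a separation taken from invasive cancers and benign lesions. Section 2 says FES has not been studied in DCIS. This stands too, so 0.74 is one scenario and not a forecast.

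**The ER-to-risk link is uneven.** Grade is one of several inputs to the clinicopathologic models. The Oncotype panel (section 5.7, Table 3) contains neither grade nor ER; its hormone-receptor gene is PR. No section says that ER-negative DCIS scores 39 or more, so for Oncotype the link is an assumption.

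**The cut-point.** A reader might infer that it must settle at the ER+/ER-negative boundary. Even in the 0.74 case it fell below all ER+ lesions only about half the time.

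**Mitigations exist.** The cap, the planned 95% intervals and the objective 4 scatter plot all help, and ER status is recorded for everyone. They limit the problem, but none yields an ER+ estimate or commits the report to one.

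**An ER+-only result is nearly uninformative.** With an interval of about 0.08 to 0.92 this is fair. It argues against replacing the pooled estimate, but not against showing the ER+ one beside it.

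**Conclusion.** The point holds as a cheap improvement. Section 12.2 items 3 and 4 plan no ER+-only estimate, although the declared follow-on use is in ER+ DCIS and up to a quarter of the sample may be ER-negative. Pooling is inferred from the absence of any ER restriction; the plan does not state it in words.

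If ER-negative lesions have low uptake and are more often higher-risk (plausible from section 2 for the models that use grade, assumed for Oncotype), the pooled AUC, cut-point and correlation may partly reflect ER status. With no association within ER+, the illustrative pooled AUC runs from about 0.50 to 0.88, and extreme splits fall outside that range. The bias vanishes when ER-negative lesions are no more often higher-risk than ER+ lesions. The pooled Spearman coefficient could reach about −0.57 at the extreme.

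With intervals this wide, the main danger for objective 3 is a misleading point estimate or cut-point; objective 4 can also reach nominal significance. The documents do not support the stronger readings that the pooled results are invalid or that about nine ER+ lesions should become the governing analysis.

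**What to change.** Keep the pooled analyses for the DCIS objectives as worded. Add to section 12.2 items 3 and 4, before results are seen:

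1. The same AUC, sensitivity and specificity (each risk model) and Oncotype correlation, with 95% confidence intervals, in ER+ subjects only, reported as descriptive.
2. ER-negative points marked on the ROC data and scatter plots.
3. A statement that any conclusion about risk stratification within ER+ DCIS will refer to the ER+ estimates.

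This needs no new patients, scans or assays: only a change of wording and one repeat of each analysis. The price is very wide intervals in about 9 to 12 ER+ subjects. There may be fewer for Oncotype, because section 5.7 limits that assay to subjects with enough remaining tissue.
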